## **II. DESCRIPTION OF THE PROJECT**

**11. Aim of the study** (brief outline with the main objectives):

As part of quality assurance in accordance with radiation protection guidelines and X-ray regulations, radiation therapists are required to provide regular follow-up care after therapeutic radiation application. As a rule, annual follow-up examinations with structured documentation of local control and side effects take place for up to 5 years after the end of therapy.

Intraoperative radiotherapy has been performed for breast cancer as an early tumor bed boost for several years in accordance with national guidelines (Sautter-Bihl et al: DEGRO practical guidelines for radiotherapy of breast cancer. Strahlenther Onkol 2007; 183:661-666). We have already published several articles on the safety and toxicity of the procedure (e.g., Wenz F, Welzel G, Blank E, Hermann B, Steil V, Suetterlin M, Kraus-Tiefenbacher U: Intraoperative radiotherapy (IORT) as a boost during breast conserving surgery (BCS) using low kV X-rays – the first five years of experience with a novel approach. Int J Radiat Oncol Biol Phys 77:1309-1314, 2010).

As part of the project, a multicenter study will now be conducted to determine whether the results we have achieved can also be achieved in regional healthcare settings. To this end, patients who receive IORT as an early tumor bed boost and are treated and followed up in accordance with the guidelines will be prospectively registered and documented. For this purpose, pseudonymized data from the other centers will be faxed to the registry center in Mannheim and evaluated by us.

**12. Planned start and expected duration of the study:** September 1, 2011

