Targeted Intraoperative Radiotherapy Boost Quality Registry (TARGIT BQR)

Statistical Analysis Procedures – 09. December 2025

(NCT01440010)

PI: [name]; MD

Oncological Outcome

Outcome variables were local recurrence, ipsilateral breast carcinoma, contralateral breast carcinoma, local lymph node metastasis and distant metastasis. Kaplan-Meier estimates were done to calculate cumulative rates for disease-free survival, local recurrence rate, local recurrence-free survival, metastasis-free survival and overall survival. For all Kaplan-Meier estimates, death was also counted as an event and not censored, except for local recurrence rate where only recurrences were counted as an event. For disease-free survival any event (death, local recurrence, metastasis, ipsilateral breast carcinoma, contralateral breast carcinoma, local lymph node recurrence) was included whatever occurred first. Eight patients had bilateral breast cancer and were counted once in case of an event of metastasis or death. The statistical analysis was performed for the endpoints of the oncological outcome in an intention-to-treat-setting using SPSS, Version 27.

Toxicity

For cumulative toxicity rates grade 2 fibrosis, breast edema, lymphedema, hyperpigmentation, retraction, and pain were documented if they occurred at least 3 times during the follow-up period. Teleangiectasia and ulceration, irrespective of their severity, were recorded as single occurrences. Data on acute and long-term toxicity were recorded. Simple frequencies, relative and absolute values, and cumulative rates were calculated. Cumulative rates were calculated based on the Kaplan-Meier method (SAS, release 9.3 and SPSS, Version 27). This is an intention-to-treat-analysis of the whole cohort. All data were collected at the study center in Mannheim. The registry closed recruitment in December 2020.

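### Does the SAP's silence on patient or breast as the unit, for the eight bilateral patients, call for a change to the plan?

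*SAP*

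**What the plan says.** The Oncological Outcome section of the SAP lists the outcomes: "Outcome variables were local recurrence, ipsilateral breast carcinoma, contralateral breast carcinoma, local lymph node metastasis and distant metastasis". From these it derives Kaplan-Meier "cumulative rates for disease-free survival, local recurrence rate, local recurrence-free survival, metastasis-free survival and overall survival". Death is an event in all of them, "except for local recurrence rate where only recurrences were counted as an event". The disease-free survival composite takes the first of several events: "death, local recurrence, metastasis, ipsilateral breast carcinoma, contralateral breast carcinoma, local lymph node recurrence) was included whatever occurred first".

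Bilateral disease appears once: "Eight patients had bilateral breast cancer and were counted once in case of an event of metastasis or death".

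In the Toxicity section, grade 2 findings of six kinds (such as fibrosis, retraction and pain) "were documented if they occurred at least 3 times during the follow-up period". Telangiectasia and ulceration need only one occurrence.

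The protocol does not mention bilateral disease or a unit of analysis. Section II, item 11 describes "annual follow-up examinations with structured documentation of local control and side effects take place for up to 5 years".

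**The concern.** The counting rule for the eight patients names two events, metastasis and death. Three matters that depend on the breast are left without a rule.

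- **Unit for local endpoints.** Local recurrence, ipsilateral carcinoma and most of the listed toxicities belong to a breast, but no denominator is given. A rule limited to metastasis and death invites the question whether these patients enter twice elsewhere.
- **Timing of the second cancer.** A second cancer present at registration is baseline disease; one that arises later is a contralateral event and ends disease-free survival. The sentence fits either case.
- **Toxicity threshold.** With two treated breasts, three findings in one breast differ from two in one and one in the other.

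If the choices mattered, a reader could not rebuild the denominators of the local endpoints, or tell whether up to eight cancers are inside the contralateral count and disease-free survival.

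**Working it through.** The documents give no event count or rate tied to this point, so there is no figure of the plan's own to reproduce. The size of the ambiguity can be bounded.

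**Inputs**
- Bilateral patients: 8 (SAP, Oncological Outcome).
- Cohort size N: 1000, the planned inpatient number (Protocol, Section II, item 13a). The SAP gives no analysed number, so N = 1000 is an assumption; 500 and 1500 are shown as a range. The same item shows 100 beside patients able to consent. With none listed as unable to consent, that does not agree with 1000, and I do not take it as the cohort size.
- Event rates of 2%, 5% and 10%: assumed.
- Visits: 5, from annual follow-up over 5 years (Protocol, Section II, items 11 and 14).

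**Step 1: second cancers counted as events or not.** The largest change in the crude disease-free survival event proportion is 8/N. It needs all eight reclassified and none with an earlier event, because only the first event counts.

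| N | 8/N, percentage points |
|---|---|
| 500 | 1.60 |
| 1000 | 0.80 |
| 1500 | 0.53 |

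At N = 1000, an assumed 5.0% would become (50 + 8)/1000 = 5.8%.

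**Step 2: patients or breasts as denominator.** Hold the number of events e fixed and compare e/N with e/(N + 8), for N = 1000.

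| Assumed rate | e/1000 | e/1008 | Difference, points |
|---|---|---|---|
| 2% | 2.000% | 1.984% | 0.016 |
| 5% | 5.000% | 4.960% | 0.040 |
| 10% | 10.000% | 9.921% | 0.079 |

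Over N = 500 to 1500 the difference runs from 0.011 points (2%, N = 1500) to 0.157 points (10%, N = 500). If the eight added breasts recur at the same rate as the others, events become e × (N + 8)/N. Divided by N + 8 this is again e/N, so the difference disappears.

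**Step 3: toxicity threshold.** The ceiling is again 8/1000 = 0.8 points for any one toxicity. For illustration, assume both breasts treated in all eight patients, independent visits and a probability p of the finding per breast and visit. Compare reaching 3 of 5 visits in at least one breast, 1 − (1 − P(X₅ ≥ 3))², with 3 of 10 pooled, P(X₁₀ ≥ 3). Multiply the difference by 8/1000.

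| p | Either breast | Pooled | Effect on cohort rate, points |
|---|---|---|---|
| 0.05 | 0.23% | 1.15% | 0.007 |
| 0.10 | 1.7% | 7.0% | 0.043 |
| 0.20 | 11.2% | 32.2% | 0.168 |
| 0.30 | 30.0% | 61.7% | 0.254 |

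Independence is a poor model for lasting findings such as fibrosis, so only the ceiling is firm. Telangiectasia and ulceration carry no repeat threshold and are unaffected.

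**Step 4: do the stated rules conflict?** With one record per patient, counting death once and treating death as an event say the same thing. Local recurrence rate is exempt from the death rule, so nothing clashes there either. A conflict would need two records per bilateral patient in the composite endpoints, which the SAP does not describe.

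**The case for a change.** The best case for a change rests on contralateral carcinoma. It is an outcome in its own right and a component of disease-free survival, its absolute count may be small, and the documents do not date the eight second cancers. The counted-once sentence would also be redundant if every endpoint used one record per patient, so its narrow wording hints at breast-level counting for local events. If breasts were analysed as separate units, correlation within a patient would need a word. Two or three sentences, with no new data, would settle all of this.

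The textual part stands: the SAP does not say these things and the protocol does not supply them. Less remains once the two timings are considered. A second cancer present at registration would need an event time of zero or less to enter the Kaplan-Meier estimate, which an analyst would hardly do. A later one is already an event under the SAP's list: "For disease-free survival any event (death, local recurrence, metastasis, ipsilateral breast carcinoma, contralateral breast carcinoma, local lymph node recurrence) was included". The diagnosis date decides which case applies, and for the ordinary reader of the rule it leaves little to choose. How much the contralateral count could change in relative terms cannot be judged, because the documents give no count of contralateral carcinomas.

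The hint of breast-level counting is an inference. If right, it points to a common arrangement: local events by breast, death and metastasis by patient. Eight patients with correlated breasts in a cohort of about 1000 would barely affect the precision of any rate. Nothing in the Toxicity section suggests adding findings across breasts.

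**Conclusion.** This is missing detail that analysts fill sensibly, and no change to the plan follows. It is confined to local recurrence rate, the breast-specific components of disease-free and local recurrence-free survival, local toxicity, and the timing of the eight second cancers. For death and metastasis the SAP gives a per-patient event rule, and only the denominator is unstated.

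At an assumed N = 1000, disease-free survival could move by at most 0.8 points, and only if all eight second cancers were counted and none of these patients had an earlier event. The choice of denominator moves assumed rates of 2% to 10% by about 0.02 to 0.08 points. Pooling the toxicity threshold across breasts cannot add more than 0.8 points to any one toxicity. These are crude proportions that ignore censoring, and they scale with 8/N if the analysed number differs.

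The SAP is dated December 2025, is written in the past tense and reports that recruitment closed in December 2020. It records an analysis already carried out in a descriptive registry, and no comparison or decision threshold in it depends on differences of this size. Writing down the unit and the timing would help a reader of the report, but it would not alter a method or an expected conclusion.

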## I. GENERAL INFORMATION

Reception stamp

1. **Date of application:** July 31, 2011
2. **Project name (English title):** TARGIT-BQR (TARGEted Intraoperative RadioTherapy – Boost Quality Control Registry)
3. **Is this a multicenter study?** Yes:  No:
4. **Specify type of study:** Quality assurance according to radiation protection guidelines

Pilot study? Comparative? Placebo? Open? Randomized? Single-blind? Double-blind?

5. **Name and address of the responsible study director in the field of medical EK II:**  

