**16. What exactly will be done with the patient/subject?**

Detailed description requested. Additional measures that are purely study-related must be clearly indicated.

What is the ratio of the expected benefits of the study to the risks associated with it?

The patient receives standard therapy and follow-up care in accordance with guidelines. No additional imaging examinations or blood samples are taken. The standard documentation is faxed to us and evaluated by us.

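### Is intention-to-treat the wrong analysis set for a registry that patients enter by receiving the IORT boost?

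*SAP*

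**What the plan says.** The SAP names the analysis population twice. Under Oncological Outcome: "The statistical analysis was performed for the endpoints of the oncological outcome in an intention-to-treat-setting". Under Toxicity: "This is an intention-to-treat-analysis of the whole cohort". It gives no definition of the term, no moment of entry, and no rule for patients whose later treatment or follow-up is incomplete. For the toxicity endpoints it adds: "Cumulative rates were calculated based on the Kaplan-Meier method".

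The protocol says who is in the cohort. Item 11 (Aim of the study) states that "patients who receive IORT as an early tumor bed boost and are treated and followed up in accordance with the guidelines will be prospectively registered". Item 16 describes what happens to them: "The patient receives standard therapy and follow-up care in accordance with guidelines", with the registry only collecting the routine documentation. Item 4 gives the study type as "Quality assurance according to radiation protection guidelines". Neither document describes a comparison arm, a random allocation or any treatment assigned by the study.

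**The concern.** Intention-to-treat normally means analysis by the treatment assigned or intended, whether or not it was given. This registry assigns nothing, and entry follows from receiving the boost. A patient for whom IORT was planned but not delivered does not appear to enter, so an analysis of the registry cannot claim to have kept her.

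Two consequences would matter if they were real.

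- A reader who takes the label literally would think that failures to deliver the boost are in the denominator. The results would then look more transferable to regional care than the design allows.
- If patients without IORT were registered after all, the toxicity denominator would contain unexposed breasts, and the reported toxicity of IORT would be too low.

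Item 11 could also be read as admitting only patients whose treatment and follow-up kept to the guidelines, which would select out deviating cases.

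**Working it through.** The documents give no figure to reproduce here. The check compares the sets and then asks what a mismatch would do to a rate.

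1. **Who is registered.** Protocol item 11 registers recipients of the boost. Let u be the share of registered patients who did not receive IORT. Under that rule u = 0.

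2. **Who is analysed.** The SAP's toxicity statement refers to the whole cohort. With u = 0, the whole cohort and the IORT-treated set contain the same patients. That treated set is the usual one for toxicity.

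3. **Is guideline adherence an entry filter?** Item 11 says registration is prospective, and item 14 gives each patient five years in the study. At registration those five years lie ahead, so adherent follow-up cannot be a condition of entry. Item 16 uses similar language simply to describe routine care, and the inclusion and exclusion items (17a and 17b) list no adherence condition. The documents therefore do not show that deviations after IORT are selected out.

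4. **Effect on a toxicity rate.** Let p1 be the rate in exposed patients and p0 the rate in any registered without IORT. Taking equal follow-up in both groups, the pooled rate is (1 − u) × p1 + u × p0, and the shortfall against p1 is u × (p1 − p0).

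| Assumed u | Assumed p1 | Assumed p0 | Pooled rate |
|---|---|---|---|
| 0 (registration rule) | 10% | not needed | 10.0%, ratio 1.00 |
| 1% | 10% | 0 | 0.99 × 10% = 9.9% |
| 5% | 10% | 0 | 0.95 × 10% = 9.5% |
| 10% | 10% | 0 | 0.90 × 10% = 9.0% |

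Only the first row follows from the documents. The others need a u that item 11 sets to zero. They also take p0 = 0, which is the worst case. The SAP's toxicity list includes breast edema, lymphedema, retraction and pain, and nothing in the documents says these arise only after IORT. With any p0 between 0 and p1 the shortfall is smaller than shown.

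5. **Effect on the question asked.** Item 11 asks whether results already obtained with the IORT boost can be matched in regional settings, and item 30 describes those earlier results in terms of safety and toxicity. The question is already conditional on having received the boost. How often a planned boost fails to be delivered is not a stated objective.

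**The case for a change.** The strongest case for acting is a dilemma. If item 11 was followed, the numbers stand but the label is wrong. If intended but untreated patients were registered, the label may fit but the toxicity denominator is wrong. The SAP defines nothing, so the documents cannot prove which holds, and a wording change would be cheap.

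The first half stands as a matter of vocabulary: intention-to-treat is a loose term for a single cohort entered by treatment. The dilemma is not complete, however. A third reading fits both documents: everyone registered after IORT is kept, whatever later deviations or losses to follow-up occur. The SAP's reference to the whole cohort points that way. It is a real and useful property, and the alternative set one would write down instead has the same content.

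The second half needs registered patients without IORT, and no text says there were any. The eight bilateral cases in the SAP might seem to leave room for an unexposed second breast. But the rule that such a patient counts once for metastasis or death is needed only if both sides have their own record, and under item 11 a record follows from a boost. Suppose even so that all eight second breasts were unexposed and free of toxicity. Added to the 1,000 inpatients planned in item 13, they would be 8/1,008 = 0.8% of breasts, and a 10% rate would read 10% × (1 − 0.0079) = 9.92%. The number actually recruited is not in the SAP, so the 1,000 is an assumption. On the 100 given in the consent line of item 13, the same worst case would be 8/108 = 7.4%, or 9.3%.

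**Conclusion.** No change to the plan follows. The label is undefined and does not suit a registry without allocation, but following the SAP as written leads to the set one would want for toxicity: all registered recipients of the IORT boost, kept regardless of what happens afterwards. The numerical effect under the protocol's own registration rule is nil.

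This rests on two assumptions: that registration followed item 11, and that the whole cohort means everyone registered. Nothing in either document contradicts them. The missing definition is one that analysts fill sensibly, and an ordinary account of the numbers registered, treated and followed up would show a reader which set was used. Replacing the term would improve the wording without altering a patient, a denominator or an estimate.

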**14. Expected duration of the study phase for each patient/subject: 5 years**

**15. Age of patients/subjects:**

Lower limit: 18 years  
Upper limit: 85 years

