**Not applicable**

**22 If the study**

- directly in the interests of patients: No
- a purely scientific purpose without direct diagnostic and therapeutic value for patients: yes
- the future development of diagnostic and therapeutic procedures: yes
- the acquisition of knowledge about the causes and prognosis of diseases: no
- Gaining insights into specific issues relating to the health status of the population: No
- Other objectives: Yes, comprehensive quality assurance

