**Not applicable**

29 Is the clinical trial investigator informed about the results of the technical safety assessment of the investigational products and the anticipated risks associated with the clinical trial? Yes

30 Have similar or comparable projects already been carried out or are they currently being carried out?

If so, with what results? Yes, single-center, see publication, high safety and low toxicity rate

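### The protocol asks about results in regional care, but the SAP specifies only pooled rates and does not say whether Mannheim's own patients are in them

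*SAP*

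**What the plan says.** Protocol item 11 (Aim of the study) gives the research question: "a multicenter study will now be conducted to determine whether the results we have achieved can also be achieved in regional healthcare settings". Item 30 identifies what those results are, answering the question on comparable projects with "Yes, single-center, see publication, high safety and low toxicity rate". No numerical benchmark is given. Item 22 lists the purpose as "Other objectives: Yes, comprehensive quality assurance", and item 14 sets the horizon: "Expected duration of the study phase for each patient/subject: 5 years".

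The SAP, under Oncological Outcome, specifies Kaplan-Meier cumulative rates for five endpoints: disease-free survival, local recurrence rate, local recurrence-free survival, metastasis-free survival and overall survival. They are analysed by intention to treat, with no centre subset. Under Toxicity it specifies frequencies and cumulative rates, and states: "This is an intention-to-treat-analysis of the whole cohort". There is no centre variable, no regional subset and no stratification.

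Three sentences bear on whose patients form the cohort:
- Item 11: "pseudonymized data from the other centers will be faxed to the registry center in Mannheim".
- Item 16: "The standard documentation is faxed to us and evaluated by us".
- SAP, Toxicity: "All data were collected at the study center in Mannheim".

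**The concern.** The question is about centres other than the originating one, whereas the specified outputs describe everyone together. If Mannheim contributes patients, its results enter both sides of the comparison: they form the benchmark, and they also make up part of the rate set against it. A worse regional result would then be partly averaged away, and the pooled rate would move towards apparent confirmation of the aim. If Mannheim contributes none, the pooled rate already is the regional rate. A reader of the two documents cannot tell which case applies.

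**Working it through.** **Who is in the cohort.** Speaking of other centres in item 11 reads most naturally as Mannheim being one of several contributors. The sentence in item 16 has no exception for Mannheim, but it is a short form answer about what is done to the patient and is thin evidence that all patients were treated elsewhere. The SAP sentence on data collection describes where data were gathered, not where patients were treated. Inclusion is therefore likely but not stated.

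**Figure to reproduce.** There is none: the documents give no event rate, margin, benchmark value or centre breakdown.

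**Inputs.**
- From the documents: N = 1000, the planned inpatient number in protocol item 13. It is not the analysed cohort, and the same item also shows 100 patients capable of consent.
- Assumed: rate in Mannheim p_M = 2%, regional rate p_R = 4%, Mannheim share w from 0% to 70%.

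**Formulas.**
- Pooled rate = w·p_M + (1 − w)·p_R.
- Fraction of the regional excess shown = (pooled − p_M)/(p_R − p_M) = 1 − w.
- Wald half-width = 1.96·√(p(1 − p)/n), with n = 1000 pooled and n = (1 − w)·1000 for the regional rate.

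For example, at w = 50% the pooled rate is 0.5 × 2% + 0.5 × 4% = 3.0%. The half-widths are 1.96·√(0.03 × 0.97/1000) = 1.1 points pooled and 1.96·√(0.04 × 0.96/500) = 1.7 points regional.

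| Mannheim share | Pooled rate | Excess shown | Half-width, pooled | Half-width, regional only |
|---|---|---|---|---|
| 0% | 4.0% | 100% | 1.2 | 1.2 |
| 10% | 3.8% | 90% | 1.2 | 1.3 |
| 30% | 3.4% | 70% | 1.1 | 1.5 |
| 50% | 3.0% | 50% | 1.1 | 1.7 |
| 70% | 2.6% | 30% | 1.0 | 2.2 |

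The fraction 1 − w does not depend on the assumed rates: it is the same for assumed Mannheim rates of 2%, 5% and 10% with regional rates 1.5 or 2 times as high.

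**Kaplan-Meier.** The identity is exact for proportions with complete follow-up and approximate for Kaplan-Meier rates, because unequal censoring changes each group's weight over time. I took constant event and censoring hazards, with pooled rate = 1 − exp(−∫ at-risk-weighted mean hazard) over 0 to 5 years. At w = 50% the fraction shown is 50% with equal censoring, 43% if 10% of Mannheim and 50% of regional patients are censored by 5 years, and 57% with those two figures reversed.

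**What a split could show.** At w = 50% the difference between regional and Mannheim rates is 2 points. Its half-width is 1.96·√(0.02 × 0.98/500 + 0.04 × 0.96/500) = 2.1 points, so the 95% CI is −0.1 to 4.1 points. At shares of 10%, 30% and 70% the CIs are −1.0 to 5.0, −0.1 to 4.1 and −0.4 to 4.4. All include zero.

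**The case against.** The strongest reply has three parts.

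First, dilution depends on a fact that nobody outside the registry has. A reader might infer that the reported rates do hide a worse regional result. The documents do not support that: they give neither the Mannheim share nor any rate. At an assumed 10% share the pooled interval (2.6% to 5.0%) and the regional one (2.7% to 5.3%) nearly coincide. This part stands, and it limits the point to what is unspecified.

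Second, this is a quality-assurance registry with no hypothesis test, margin or duty to report by centre. A whole-cohort rate beside the published single-centre results is a legitimate, if coarse, descriptive answer. The SAP is also a short past-tense summary dated 9 December 2025, after recruitment closed in December 2020, so a split may have been made without being mentioned. Both remarks are fair. They do not remove the gap, because following the SAP as written would give no regional estimate if Mannheim is included.

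Third, a split would not settle whether the results were achieved. Besides the differences shown above, a comparison with the earlier series carries that series' own error. With an assumed 150, 300 or 600 earlier patients at 2%, and 500 regional patients at 4%, the CI for the difference is −0.8 to 4.8, −0.3 to 4.3 or −0.1 to 4.1 points. This stands too: the gain is an undiluted regional point estimate, not a test.

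**Conclusion.** The point holds as a gap in specification. The aim concerns regional care, only pooled rates are specified, and the cohort's make-up by centre is not stated. The wording of item 11 suggests that Mannheim's patients are included. If they are, the pooled rate shows about 1 − w of any regional excess: 90% of it at a 10% share and 50% at a 50% share. These sizes rest on assumed shares; the example rates of 2% and 4% and the use of N = 1000 are assumptions as well. If Mannheim's share is zero, nothing is diluted.

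A reader might go further and conclude that the documents contradict each other on who enrols, or that the regional result has been masked. Neither follows. The passages leave enrolment open rather than in conflict, and no result by centre is given.

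**What to change.** State in the SAP how many patients each centre contributed and whether Mannheim's own patients are in the analysed cohort.

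If they are, add wording such as:

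> Beside the pooled rates, 5-year cumulative rates with 95% CIs are given for all centres other than Mannheim and separately for Mannheim, for local recurrence rate, disease-free, local recurrence-free, metastasis-free and overall survival, and each toxicity endpoint. They are set beside the earlier single-centre results. The split is post hoc and descriptive; no significance test is made. Differences may reflect case mix or calendar period. CIs that ignore clustering by centre may be too narrow, and the earlier results have their own sampling error.

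Five years is offered because it is the per-patient duration in protocol item 14; another time point would serve if stated.

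If Mannheim's patients are not included, one sentence saying that the whole-cohort rates are the regional rates is enough.

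The cost is low. With five oncological rates and the eight toxicity endpoints that the SAP names, the split adds (5 + 8) × 2 = 26 rates. It needs no new data collection provided that centre is recorded for each patient, which the documents do not state. The downside is more tables and wider regional intervals: a half-width of about 1.7 points against 1.1 pooled at an assumed 50% share and N = 1000.
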